#### 7.1 HYPOTHESES/RESEARCH QUESTIONS:

This is a pilot study and thus our goal is to explore the feasibility of an appropriately powered clinical study, which would investigate the utility of the Pain Medication and Mental Health DNA Insight TM test to improve pain management of patients with chronic pain. Our goal is to explore how providers and patients will respond to this test and we intend to use our findings to generate hypotheses and preliminary data for a robust, fully powered clinical trial in the future.

Our research questions are:

How does the use of the Pain Medication and Mental Health DNA Insight TM test affect provider satisfaction, certainty and confidence in dosing of opioid and non-opioid analgesics?

How does the use of the Pain Medication and Mental Health DNA Insight TM affect patient

WAMC Protocol Template Revised 3 January 2014

Page 12 of 34

Protocol Title: Patient and provider confidence and satisfaction with the clinical use of CYP genetic variability analysis to guide analgesic treatment: A randomized, controlled pilot study using the Pain

Medication and Mental Health DNA InsightTM test.

Initial Date Submitted: 02/10/2015 Revision Date: 31 August 2016

satisfaction, certainty and confidence in pain management plan?

How does the use of the Pain Medication and Mental Health DNA Insight TM test affect pain related patient-reported outcomes, including DVPRS, PROMIS and BPI scores?

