#### 7.3 DESIGN

#### 7.3.1 Design type:

This is a prospective, randomized, controlled, observational pilot study analyzing both providers' and patients' perceptions and responses to the DNA Insight test. For this study there will need to be a total of twelve provider groups to be enrolled and 4-8 of each provider's patients will be enrolled in the study. Enrollment will continue of providers until up to 12 providers and 48 patients have been enrolled in the study. Therefore twelve to sixteen military health system primary care providers will need to be consented due to withdrawal of providers prior to

Page 13 of 34

Protocol Title: Patient and provider confidence and satisfaction with the clinical use of CYP genetic variability analysis to guide analgesic treatment: A randomized, controlled pilot study using the Pain

Medication and Mental Health DNA Insight $^{\text{TM}}$  test.

Initial Date Submitted: 02/10/2015 Revision Date: 31 August 2016

referring patients. A total of 48 patients will be enrolled, 4-8 patients for each of the actively enrolled providers (12- 16 providers and 48 patients total). Each provider's patients will be randomized into delayed treatment (Group A) or immediate treatment (Group B) at a 1:1 ratio. Each participating provider will agree to order and interpret a Pain Medication and Mental Health DNA InsightTM test. Results for patients in Group A will be given to the provider with a 3 month delay. Those in the 3 month delay will serve as a comparison group for the period prior to receiving intervention. Results for patients in Group B will be given to the provider without delay, 2-3 weeks after saliva sample collection. The provider will use the results of the Pain Medication and Mental Health DNA InsightTM test to evaluate whether changes of medications are indicated based on the individual patient's genetic profile. A measure of the provider's certainty, confidence, satisfaction, perception of care and global impression of change will be assessed at baseline, prior to obtaining the test results, and after obtaining the test results, as outlined in the data collection section. Patients' pain related self-reported outcomes, certainty, confidence and satisfaction will be assessed at baseline, prior to obtaining the DNA InsightTM test results, and after receipt and implementation of the test results, as described in the data collection section of the protocol.

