#### 8.0 DATA ANALYSIS:

For this two-group design, a variety of self-report measures (confidence, certainty, etc.) will be taken up to a maximum of 8 repeated measures, including a baseline measure prior to the intervention. Given this variability where time is not a fixed factor insofar there may be variation for number of measures by individual and/or group a mixed linear modeling (or sometimes referred

Protocol Title: Patient and provider confidence and satisfaction with the clinical use of CYP genetic variability analysis to guide analgesic treatment: A randomized, controlled pilot study using the Pain

 $\label{eq:medication} \mbox{Medication and Mental Health DNA Insight}^{\mbox{\scriptsize TM}} \ \ \mbox{test.}$ 

Initial Date Submitted: 02/10/2015 Revision Date: 31 August 2016

to by the umbrella term: multilevel modeling-MLM) analysis will be conducted. The advantage of a MLM approach is that it is sufficiently flexible insofar inter-individual variability on (1) time and (2) number of measures can be readily accommodated. Moreover, in the context of a longitudinal design interindividual differences in intraindividual trajectories can be captured.

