When conducting a MLM analysis, the assumption is that there is a nested structure, and particularly for event-based studies, time (level 1-microlevel) will be nested within the patient (level 2- individual). For this study there are 12 provider groups with 4 patients nested within the groups, hence this could be cast as a 3-level model (time nested within patient nested within provider). However, one caveat is this is a very small sample size for MLM, and power may be a significant issue. The viability of increasing the sample size or aggregating levels (if deemed appropriate insofar it does not compromise the integrity of the design) will be explored. A sequence of models will be examined, with the unconditional means model (no predictors) as the starting point, serving to compute the unconditional intraclass correlation coefficient (ICC), and hence capturing the extent of between-patient variability. Subsequent models will entail adding a variable that captures time, and then at the macro-level introducing the grouping (experimental vs. control) variable. If deemed appropriate, all time-invariant and time-varying predictors will be testing for significance ( $\alpha = .05$ ) and moreover, the stochastic parameters (i.e., variance components) will also be examined:  $\underline{u}_0$  and possibly  $\underline{u}_1$  where  $\underline{u}_0$  is the random coefficient for the intercept (i.e. initial basis) and  $u_i$  is the random coefficient for the slope. For the single-item ordinal-level outcomes the cumulative logit link function will be employed using residual maximum likelihood (REML) as the default estimator (otherwise the identity link function will be used for continuously measured outcomes).

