Selection of the best fitting model will be guided not only by the change in magnitude of the variance components, represented in part by the pseudo r statistic, but also information-theoretic indices such as the Akaike Information Criterion (AIC) or Bayesian Information Criteiron (BIC), of which the model with the lower value evinces better fit. All MLM analysis will be conducted using the HLM7.01 software. Data cleaning, testing of assumptions and descriptive analysis will be performed in SPSS v. 22 or Stata v. 11.0. Moreover, as a basis of comparison (again keeping in mind small sample size) generalized estimating equations (GEE) will also be considered, with an unstructured working correlation matrix stipulated as the error variance/covariance matrix (though alternatives such as autoregressive with lag 1 (AR1) may be considered).

As for testing concordance of patients and caretakers, correlations will be computed as well as intraclass correlation coefficients (ICC) so as to assess the level of relationship between the patients and providers on like-items.

Commented [1]: Can [name] address this sentence?

Protocol Title: Patient and provider confidence and satisfaction with the clinical use of CYP genetic variability analysis to guide analgesic treatment: A randomized, controlled pilot study using the Pain

Medication and Mental Health DNA Insight  $^{TM}\;\; test.$ 

Initial Date Submitted: 02/10/2015 Revision Date: 31 August 2016

References: See Section 6.1

A database will be created in REDCap (Research Electronic Data Capture) after IRB approval. REDCap is a secure, web-based application for building and managing online surveys and databases. The data will be housed and secured on Defense and Veteran Center for Integrative Pain Management (DVCIPM) servers. Each patient will be allocated a study ID number, 01-48 and providers will be assigned study ID numbers 101-112, when they sign a consent form, and thereafter will be referred to by that number in the database. Investigators and research staff will have secure password protected access to RedCap in order to enter data.

The REDCap data will be extracted and sent to an outside DVCIPM statistician, for analysis. PHI will be removed before sending to the statistician.

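### Section 8.0 does not protect the randomised group term from fit-based model selection; if reporting follows selection, the retained estimate is biased away from zero

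*Combined protocol and SAP*

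**What the plan says.** Section 8.0 (Data Analysis) sets out a build-up: "A sequence of models will be examined, with the unconditional means model (no predictors) as the starting point". A time variable is added next, and then the group variable. A choice follows: "Selection of the best fitting model will be guided not only by the change in magnitude of the variance components", with pseudo-R² as part of that measure, but also by information criteria such as AIC or BIC, "of which the model with the lower value evinces better fit". Predictors are to be tested at α = 0.05 where this is judged appropriate.

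The section names no primary outcome and no primary model. It does not say whether AIC or BIC decides when they disagree, and it does not say that the group term is kept regardless of fit.

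Two other places bear on this. In section 7.2, Aims 2 and 3 call for between-group comparisons and do not make them conditional on model fit. Section 7.1 says that the findings are meant to "generate hypotheses and preliminary data for a robust, fully powered clinical trial in the future".

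**The concern.** The last step of the build-up adds the randomised comparison itself. A rule that picks the best-fitting model from that sequence therefore treats the comparison as optional, separately for each outcome. In a small study the group term is more likely to survive when chance has enlarged the estimate. If only surviving estimates are reported, they overstate the effect on average, and their p-values and intervals are computed as though no selection had taken place. Small or null differences would drop out of the results.

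The cause is the selection, not the estimator, so refitting by ML instead of REML does not remove it. At stake is whether this pilot reports weak and null group differences as fully as strong ones.

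**Working it through.** The documents state no power, effect size, SD or correlation, so there is no planned figure to reproduce. The only internal check is 12 × 4 = 48 patients, which agrees ("A total of 48 patients will be enrolled, 4-8 patients for each of the actively enrolled providers"; "For this study there are 12 provider groups with 4 patients nested within the groups").

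**Inputs from the documents**
- 48 patients, "randomized into delayed treatment (Group A) or immediate treatment (Group B) at a 1:1 ratio", hence 24 per arm.
- Group A receives its results at visit 3 (Table 1: Visit Chart), so visits 1 and 2 precede that point.

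**Assumptions**
- One parameter is added for group.
- AIC or BIC is applied strictly.
- The estimate is approximately normal.
- True effects are 0.2, 0.4 and 0.8 SD.
- The standard error is 0.19 to 0.26 SD. A correlation of 0.6 between visits gives both ends for the mean of two visits. Without baseline adjustment, √[(2/24) × (1 + 0.6)/2] = 0.258. With it, √[(2/24) × (0.8 − 0.36)] = 0.191.

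**Thresholds.** Adding one parameter lowers the criterion when the likelihood-ratio chi-square exceeds 2 (AIC) or ln n (BIC). With n = 48 patients, ln 48 = 3.87. The group term is kept when |z| > c, with c = √2 = 1.414 (AIC) or √3.87 = 1.968 (BIC).

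**Formulas.** Let m = true effect / SE.
- P(keep) = Φ(m − c) + Φ(−m − c).
- Mean of kept z = m + [φ(c − m) − φ(c + m)] / P(keep).
- Inflation = mean of kept z / m.

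**Example** (AIC, 0.4 SD, SE 0.26): m = 1.538. P(keep) = Φ(0.124) + Φ(−2.95) = 0.55. The mean kept estimate is 0.584 SD, and 0.584/0.4 = 1.46.

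| True effect | Rule | Kept, SE 0.19 to 0.26 | Kept estimate ÷ truth |
|---|---|---|---|
| 0.2 SD | AIC | 37% to 27% | 1.9 to 2.4 |
| 0.4 SD | AIC | 76% to 55% | 1.20 to 1.46 |
| 0.8 SD | AIC | 99.7% to 95% | 1.00 to 1.03 |
| 0.4 SD | BIC, n = 48 | 55% to 33% | 1.34 to 1.71 |

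If BIC counts records instead of patients, three visits (0 to 2) give n = 48 × 3 = 144. At 0.4 SD, group is then kept in 45.1% to 24.5% of trials, at 1.42 to 1.83 times the truth.

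**No true effect.** AIC keeps group with probability P(χ²₁ > 2) = 0.157. Among those kept, 0.05/0.157 = 32% have a nominal p below 0.05. Under BIC with n = 48, every kept estimate does, because 3.87 exceeds 3.84.

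**Cross-check by ML mixed models.** 1,000 trials per effect were simulated with 48 patients, 7 visits, an assumed ICC of 0.5, and time-only compared with time-plus-group. The SE was about 0.21. AIC kept group in 33% of trials at 0.2 SD (2.1 times the truth), 81% at 0.5 SD (1.14 times) and 99% at 0.8 SD (1.0 times). The bias is therefore present under ML.

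**The case against.** Four objections have weight.

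1. **Withholding is not stated.** A reader might infer that the group effect will be reported only when it is large by chance. The documents do not say so. The group model is fitted for every outcome as part of the sequence, and Aims 2 and 3 call for the comparison whatever the fit. This stands: the bias must be stated conditionally. It does not remove the gap, because section 8.0 does not say which model's results are reported.

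2. **The rule is not mechanical.** Fit indices only guide the choice, alongside variance components, and no deletion threshold is written. This also stands. The percentages describe a strict rule that the plan does not contain.

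3. **Nothing is said to be handed on.** A reader might infer that an inflated effect size will make the next trial too small. Section 7.1 promises hypotheses and preliminary data; it names no effect size and no sizing rule. As illustration only, a trial planned for 80% power on an effect 1.46 times too large has real power Φ(2.80/1.46 − 1.96) = 48%. If dropped effects were counted as zero, the average would instead be too small: at 0.4 SD under AIC, 0.755 × 0.479 = 0.36 to 0.551 × 0.584 = 0.32.

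4. **The size depends on the truth and on what the term measures.** At 0.8 SD the AIC bias is 0% to 3%. A group main effect fitted over visits 0 to 2 also averages in baseline, where no difference is expected. In a simulation with a true access effect of 0.5 SD, that term averaged 0.34. AIC selection raised it 1.58 times, to 1.58 × 0.34 = 0.54, which is only 1.07 times the access effect. Selection bias and dilution can thus partly offset each other, which is no reason to rely on either.

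**Conclusion.** The point holds in conditional form. Section 8.0 leaves the randomised comparison open to deletion for each outcome, and nothing there secures what Aims 2 and 3 require. If reporting follows selection, the bias in the kept estimate is large for small true effects, moderate near 0.4 SD and close to nil under AIC at 0.8 SD, as tabulated. These sizes rest on an assumed standard error, assumed effects, a one-parameter group term and strict use of AIC or BIC. A group-by-time term would change the thresholds but not the mechanism.

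The documents do not support the stronger readings that non-selected estimates will be withheld, or that an inflated effect will size the later trial.

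**What to change.** In section 8.0, state that time and the randomised group/access terms stay in every outcome model whatever the AIC, BIC, pseudo-R² or p-value, and that their estimates are reported with 95% CIs for every outcome. Limit fit-based selection to the random-effects and covariance structure, for example random intercept only versus random intercept and slope.

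This removes the selection bias from the group estimate. It does not remove the imprecision: with the assumed standard errors the 95% CI is about ±0.37 SD (1.96 × 0.19) to ±0.51 SD (1.96 × 0.26), but it is then visible for every outcome. The cost is a change of wording, with no extra patients, visits or data. The downside is that some reported models will have a slightly worse fit index.

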# **7.2 SPECIFIC AIMS/SIGNIFICANCE:** Specific Aims

- 1. Examine trends in provider decisions in prescribing analgesics and modifying analgesic treatment plans and provider outcomes for satisfaction, certainty and confidence in dosing of analgesics with and without access to Pain Medication and Mental Health DNA Insight TM genetic testing results.
- 2. Examine trends in patients' satisfaction, certainty and confidence in dosing of analgesics between patient groups whose providers had access to Pain Medication and Mental Health DNA Insight TM genetic testing results and those whose providers did not have access to the genetic information.
- 3. Compare patient-reported pain and mental health outcomes between patient groups whose providers had early access to Pain Medication and Mental Health DNA Insight TM genetic testing results to those who had delayed access in the control period and subsequently following later access to the results.

The general aim of this pilot study is to assess the utility of a test that analyzes the DNA of chronic pain patients to determine their metabolic response to common analgesics, anti-depression and anxiolytic medications, to improve provider and patient confidence and satisfaction with the pain treatment plan. The results of the DNA analysis will help guide providers to change or continue the current analgesic regimen. This concept is known as "personalized" or "precision" medicine - the ability to treat patients based on their genetic profile in order to maximize therapeutic effect and minimize or eliminate unwanted side effects.

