# Visits 1-6 (Group A receives test results at visit 3, Group B receives test results at visit 1)

Before visit with the provider

- DVPRS, PROMIS short forms for pain interference, depression, anxiety, BPI perception of pain relief item
- patient perception of care
- patient global impression of change

After visit with the provider

certainty, confidence, satisfaction

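### Section 8.0 lets AIC/BIC compare models with different fixed effects but names only REML and requires no full-ML refit; if REML values are used for continuous outcomes, the comparison depends on how the outcome is scored

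*Combined protocol and SAP*

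**What the plan says.** All of the following is in Section 8.0 (Data Analysis).

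- **Model sequence.** It starts from a model without predictors. Then: "Subsequent models will entail adding a variable that captures time, and then at the macro-level introducing the grouping (experimental vs. control) variable". The candidates therefore differ in their fixed effects.
- **Estimator.** For single-item ordinal outcomes, "the cumulative logit link function will be employed using residual maximum likelihood (REML) as the default estimator". The parenthesis that follows covers the rest: "otherwise the identity link function will be used for continuously measured outcomes". It changes the link and gives no estimator.
- **Selection.** "Selection of the best fitting model will be guided not only by the change in magnitude of the variance components", with a pseudo r-squared as part of that, and also by the "Akaike Information Criterion (AIC) or Bayesian Information Criteiron (BIC), of which the model with the lower value evinces better fit".
- **Other routes.** Predictors may be tested at alpha = .05 if that is judged appropriate, random intercept and possibly slope variances are examined, and GEE is considered as a comparison.
- **Software.** "All MLM analysis will be conducted using the HLM7.01 software".

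The plan does not mention full ML, an ML refit, or limiting AIC/BIC to models that share the same fixed effects.

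**The concern.** A REML likelihood is the likelihood of what remains after the fixed effects are removed. Models with different fixed effects remove different things, so their REML values describe different data and cannot be ranked by AIC or BIC. One symptom is dependence on units: the same data scored on a different scale can give a different ranking.

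This matters because Aims 2 and 3 in Section 7.2 are comparisons between groups, and group enters at the last named step of the sequence. Section 7.3.6 lists several instruments. Outcomes on different scales would face different hurdles for the group term even if nobody rescored anything. Section 7.1 says the pilot is to supply hypotheses and preliminary data for a full trial, so an artefact of selection could be carried forward.

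The ordinal items raise a different problem. A cumulative-logit model has no ordinary REML likelihood, and AIC/BIC from a pseudo-likelihood is not comparable across models.

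**Working it through.** The plan gives no figure to reproduce here, so the check is algebra followed by a numerical confirmation.

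**Inputs from the documents.** Section 8.0 gives 12 provider groups with 4 patients each, so 12 × 4 = 48 patients. Section 7.3.6 lists Visits 0 to 6, so 48 × 7 = 336 observations. Section 8.0 allows up to 8 measures, which would give 48 × 8 = 384. The plan does not say which n enters BIC.

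**Step 1: effect of scale under REML.** With n observations and p fixed effects,

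−2 log REML = (n − p) ln 2π + ln|V| + ln|X′V⁻¹X| + r′V⁻¹r (some forms also subtract ln|X′X|).

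Multiply the outcome by k. V becomes k²V, so ln|V| gains 2n ln k, ln|X′V⁻¹X| loses 2p ln k, and the last term is unchanged. The total change is 2(n − p) ln k. A model with one more fixed effect gains 2 ln k less, so the gap moves by 2 ln k in its favour (against it if k < 1). ln|X′X| does not involve the outcome, so the result holds in either form and for any random-effect structure.

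**Step 2: the same under ML.** Every model changes by 2n ln k, so the gap moves by 0.

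**Step 3: size against the penalties.**

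- k = 10: 2 × 2.3026 = 4.61 per term, or 9.21 if group and group-by-time enter together.
- k = 8 (item sum versus item mean, assuming that SF8a in the PROMIS form names means eight items): 2 × 2.0794 = 4.16.
- Penalty per term: AIC 2; BIC ln 48 = 3.87, ln 336 = 5.82 or ln 384 = 5.95.

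A tenfold change of scale thus exceeds the AIC penalty and the BIC penalty with n = 48, but not the BIC penalty with n = 336 or 384.

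**Step 4: numerical confirmation.** One simulated data set had 12 providers × 4 patients × 7 visits. The assumed inputs were patient SD 1.5, provider SD 0.6, residual SD 1.5, slope −0.04 per visit and group effect −0.3. The table shows AIC for time plus group minus AIC for time alone; negative favours adding group.

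| Fit | k = 0.1 | k = 1 | k = 10 |
|---|---|---|---|
| REML without ln\|X′X\| | +6.14 | +1.54 | −3.07 |
| REML with ln\|X′X\| | +1.71 | −2.90 | −7.50 |
| ML | +1.54 | +1.54 | +1.54 |

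Each tenfold step moves either REML row by 4.61 and leaves ML unchanged. Both REML rows change sign within this range. At k = 1 the two REML forms also disagree, by ln(336 × 0.25) = ln 84 = 4.43; the documents do not say which form the software reports.

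**Step 5: frequency, as illustration only.** I simulated 500 two-level data sets per scenario, with patient SD 1.6, residual SD 1.5 and group effects of 0, 0.3 and 0.6. They used REML without ln|X′X| and n = 336 in BIC. The index was the sole rule, over four models including group-by-time. Moving from 0–10 to 0–100 scoring changed the AIC choice in 89–99% of data sets and the BIC choice in 12–40%. Moving to 0–1 scoring changed them in 7–26% and 1–6%. Under ML no choice changed.

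**The case against.** The strongest reply is that Section 8.0 never says REML is used for continuous outcomes. It names REML only where the outcomes are ordinal, and there relabelling ordered categories leaves the cumulative-logit likelihood unchanged, so the scoring argument has no force. Calling REML a default also leaves ML open. This stands as a limit: the scoring problem is conditional on REML being used for the continuous outcomes. It does not remove the point, because no other likelihood estimator is named and nothing requires ML.

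Second, the plan has other ways to judge the group term. A Wald-type test at alpha = .05 is the same on any scale of a continuous outcome, since estimate and standard error both scale by k. A pseudo r-squared is a ratio of variances, so k cancels. GEE may be run alongside. This also stands, and it limits the consequence.

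Third, nobody proposes multiplying a score by 10, and the reversals come from simulated data. That is true, but the 2 ln k shift needs no assumed effect, and the planned instruments need not share a scale.

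A reader might infer that the group comparison is invalid, or that group will be dropped on a higher AIC. The documents do not support this: AIC/BIC only helps guide selection, and no text says that the group estimate is withheld. A reader might also infer that all use of REML-based AIC is wrong. It is valid for comparing random-effect structures when the fixed effects are identical.

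**Conclusion.** The point holds as a gap in specification that permits an invalid comparison. Section 8.0 uses AIC/BIC across models with different fixed effects, names only REML, and does not require an ML refit.

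For continuous outcomes, if REML values are used, the comparison moves by 2 ln k per added term. That size is exact and needs no assumption about variances or effects. Whether a particular choice would reverse depends on the data, the index, the n used in BIC and the REML form, so the simulated percentages are not a property of this trial. What HLM7.01 reports is not in the documents; if the linear models are fitted by full ML, the problem does not arise for them.

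For cumulative-logit outcomes the objection is to pseudo-likelihood AIC/BIC, not to scoring.

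The plan should be changed, but the consequence is moderate: AIC/BIC is one guide among several, and Section 7.1 presents the study as a hypothesis-generating pilot.

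**What to change.** State in Section 8.0:

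1. Full ML is used whenever AIC or BIC compares models with different fixed effects. REML is kept for comparing random-effect structures with identical fixed effects and for the final continuous-outcome estimates.
2. For cumulative-logit outcomes, AIC/BIC is used only from a true likelihood fit, for example Laplace or adaptive quadrature. Otherwise it is not used for them.

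The first item costs a sentence and a refit. The second may need software other than HLM7.01, which would mean amending the commitment to that program; dropping AIC/BIC for these outcomes avoids this. Data collection, visits and patients are unaffected.

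Separately, and equally under ML: because Aims 2 and 3 are group comparisons, always report the early-versus-delayed contrast for the period before Group A receives results, with a 95% CI, whatever the fit indices show. Section 7.3.6 has "Group A receives test results at visit 3, Group B receives test results at visit 1". By the visit order there and in Section 7.3.4, that period is Visits 2–3 for forms completed before a visit and Visits 1–2 for forms completed after it. Access therefore differs at 2 of 7 occasions. A single constant group effect over Visits 0–6 would capture 2/7 = 29% of an access effect that is immediate, constant and equal in both groups (an assumption). The contrast should therefore come from a group-by-time or time-varying access term. Section 8.0 already allows time-varying predictors, so this is a matter of naming the term.
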